## 1.0 List of Abbreviations

Abbreviation	Definition
AHF	Acute Heart Failure
AE	Adverse Event
BID	Twice daily
BMP	Basic Metabolic Panel
BNP	Brain Natriuretic Peptide
BUN	Blood Urea Nitrogen
CC	Coordinating Center
CPET	Cardiopulmonary Exercise Test
CFR	Code of Federal Regulations
CRF	Case Report Form
DCRI	Duke Clinical Research Institute
DSMB	Data Safety Monitoring Board
ECG	Electrocardiogram
eCRF	Electronic Case Report Form
ED	Emergency Department
EDC	Electronic Data Capture
EE	Expedited Event
EF	Ejection fraction
eGFR	Estimated Glomerular Filtration Rate
ER	Emergency Room
FDA	Food and Drug Administration
GFR	glomerular filtration rate
HF	Heart Failure
HFCRN	Heart Failure Clinical Research Network
HFN	Heart Failure Network
HFpEF	Heart Failure with preserved Ejection Fraction
HFrEF	Heart Failure with reduced Ejection Fraction
ICF	Informed Consent Form
ICH	International Conference on Harmonization
IND	Investigational New Drug
IRB	Institutional Review Board
ITT	Intention To Treat
IV	Intravenous
JVP	Jugular Venous Pressure
NHLBI	National Heart, Lung and Blood Institute
NRS	Numerical Rating Score
NT-proBNP	N terminal pro-B-type natriuretic peptide
NYHA	New York Heart Association
PO	By mouth
QD	Once daily
SAE	Serious Adverse Event
SAR	Suspected Adverse Reaction
SQ	Subcutaneous

## 2.0 EXECUTIVE SUMMARY

Title	SUBQ-HF Pilot: Subcutaneous Furosemide in Acute Decompensated Heart Failure
Indication	Patients hospitalized with acute decompensated heart failure.
Location	Approximately 3-5 clinical centers in the United States
Brief Rationale	
Most Acute Heart Failure (AHF) hospitalizations are related to congestion, and the primary inpatient treatment modality is parenteral loop diuretics. The average length of stay for an AHF hospitalization in the US is 5.5 days. After initial stabilization, many patients remain in the hospital for several days with a primary goal of additional decongestion with IV loop diuretics. A novel subcutaneous furosemide pump has been developed that allows patients to self-administer the equivalent of 80 mg of IV furosemide over a 5-hour period outside of the hospital setting. Existing data suggest that this approach provides bioavailability similar to that of IV furosemide injection. The clinical utility of this approach in a real world AHF population has not been evaluated.

Primary Objective	The Pilot study is designed to evaluate the overall safety and feasibility of a strategy based on subcutaneous delivery of furosemide. It will be used to inform the subsequent evaluation phase of the study (separate protocol).
Patient Population	Patients hospitalized for AHF who have had at least 24 hours of inpatient therapy and are hemodynamically stable, but still have objective signs and symptoms of congestion necessitating ongoing parenteral diuretic therapy.
Study Design	
Multi-center, open-label, pilot study conducted in 2 phases. Each phase will enroll 20 subjects that will be used to inform the study design of the SUBQ-HF Study (approximately 300 evaluable patients randomized to either usual inpatient care or early discharge with home subcutaneous furosemide for 2-7 days).
 
Inpatient Pilot Phase:
 
Eligible in-patients will be approached for participation. Subjects who consent for participation will be treated with subcutaneous furosemide for 48 hours, during which they will remain in the hospital. This will be primarily a safety and feasibility assessment. There will be no formal hypothesis tested, and statistical analysis will be descriptive in nature.
 
Outpatient Pilot Phase:
 
Eligible in-patients will be approached for participation. Subjects who

consent for participation will be instructed on use of device, discharged to home and treated at home with subcutaneous furosemide for 1-7 days. This will be primarily a safety and feasibility assessment. There will be no formal hypothesis tested, and statistical analysis will be descriptive in nature.

**Intervention**

Inpatient pilot: A strategy of subcutaneous furosemide for 48 hours inpatient.

Outpatient pilot: A strategy of subcutaneous furosemide for 1-7 days post discharge

## **3.0 INTRODUCTION**

### ***3.1 Background and Significance***

Hospitalization for acute heart failure (AHF) is a major clinical event in the natural history of heart failure, associated with a high morbidity and mortality over the subsequent months, high health care utilization, and costs. AHF is the most common cause of hospital admission in patients over age 65, accounting for 1,000,000 admissions, over 6 million hospital days, and \$12 billion in costs annually. The prognosis of patients admitted with AHF is dismal, with a 20-30% readmission rate and a 20-30% mortality rate within six months after admission. Approximately 75% of health care spending on heart failure is driven by the costs of inpatient care, and costs of heart failure care are projected to more than double by 2030^3. Given these facts, AHF has become a major focus of health care reform and public policy. Most AHF hospitalizations are for signs and symptoms of congestion, and successful decongestion is a central therapeutic goal of a heart failure hospitalization. The vast majority (> 90%) of AHF patients are still treated with loop diuretics as the primary therapy, and the need for ongoing parenteral diuretics is a primary determinant of length of stay.

Despite the utility of loop diuretics in relieving congestion in most AHF patients, data suggest that many AHF patients have persistent congestion at the time of hospital discharge, whether overt (symptoms and signs) or hemodynamic (elevated filling pressures). Persistent congestion has been shown in multiple studies to contribute to high readmission rates. However, the average length of stay for an AHF hospitalization in the United States is approximately 6 days, and even longer hospitalizations are observed in Europe and Asia. Data from the ASCEND-HF study suggest that higher length of stays are associated with lower risks of readmission, even after adjustment for differing periods of time at risk for rehospitalization. While prolonged use of parenteral diuretics may improve decongestion and decrease risk of rehospitalization, but this strategy is limited by patient factors as well as cost to the health care system (typical cost heart failure hospitalization is ~ \$2500/day in the United States). An alternative system of parenteral loop diuretic delivery via a subcutaneous furosemide pump may allow parenteral loop diuretic use outside the hospital system in selected patients. Patients undergoing parenteral diuresis at home rather than in hospital may experience greater overall activity, improved sleep, and better overall well-being compared to being hospitalized. Outpatient parenteral diuresis may allow for more complete decongestion which could decrease readmission rates. Overall, the treatment strategy could potentially result in fewer hospital days, lower costs, lower rates of readmission, greater patient satisfaction and substantial public health impact.

### ***3.2 Preliminary Data***

Furosemide is traditionally administered orally or via intravenous injection. Variability in oral bioavailability of furosemide, particularly in volume overload states, is a known limitation of oral administration and contributes to the well-described clinical phenomenon of decreasing

effectiveness of oral furosemide in the days leading up to AHF hospitalization. Intravenous furosemide is effective at initiating diuresis in most patients but is limited to use in hospital or in specialized clinics. From a pharmacokinetic standpoint, furosemide infusion has theoretical advantages over IV bolus infusion, although the DOSE trial did not suggest a clinically important difference between these two strategies as initial therapy in AHF patients. The device to be tested in this trial, the SC2Wear pump (subcutaneous pump) utilizes a reformulated neutral pH formulation of furosemide for subcutaneous delivery. The subcutaneous pump is designed to deliver a total of 80mg of parenteral furosemide over a period of 5 hours via subcutaneous injection (30 mg in hour 1, then 12.5 mg/hour over the next 4 hours) utilizing a reusable, subcutaneous delivery system (**Figure 1**).

[figure not shown]
**Figure 1. SC2Wear furosemide pump.**

Small preliminary studies examined the pharmacokinetics and pharmacodynamics of the furosemide delivery via a subcutaneous pump compared to oral furosemide or IV furosemide.

[figure not shown]
In a preliminary study of 10 stable (NYHA class II heart failure patients), 80mg subcutaneous furosemide dose achieved similar peak furosemide level ( $C_{max}$ ), longer half-life ( $t_{1/2}$ ), and greater total exposure (AUC) compared to a single 80mg oral dose (**Figure 2**).

**Figure 2. Plasma furosemide levels for oral furosemide and subcutaneous furosemide.**

In a pharmacodynamic study of 80mg IV furosemide given as two 40mg IV pushes 2 hours apart (the FDA label dosing for IV furosemide) vs. 80mg subcutaneous furosemide produced similar diuretic effect over 8 hours (**Figure 3**). These data support the concept that subcutaneous delivery of furosemide can achieve results comparable to intravenous administration. The clinical utility of this approach has not been tested in AHF population. The goal of the SUBQ-AHF study is to test the ability of a treatment strategy utilizing the subcutaneous pump in selected AHF patients to improve the total days alive and out of the hospital within the 30 days after randomization, as well as lower overall costs of care.

**Figure 3. Pharmacokinetics and diuresis from 80 mg furosemide via subcutaneous pump vs 80mg IV furosemide given as two 40mg boluses separated by 2 hours**

## 4.0 OBJECTIVES

### 4.1 Primary Objectives

To determine if a strategy of a novel subcutaneous delivery of furosemide is safe and feasible in patients with AHF.

#### OUTCOME DETERMINATIONS

The analysis of data from the Pilot Phase will be primarily descriptive in nature and there will be

no formal hypothesis testing.

## **5.0 BASIC STUDY DESIGN**

SUBQ-HF Pilot is a multicenter clinical trial of selected AHF patients with persistent congestion after initial stabilization. Broadly speaking, the pilot phase is designed to evaluate the overall safety and feasibility of a strategy based on subcutaneous delivery of furosemide. The pilot phase will consist of an inpatient and outpatient pilot occurring as described below and will be followed by review of data by the HF Network Steering Committee and Data Safety Monitoring Board. The same inclusion and exclusion criteria will be used for both phases of the pilot.

### **5.1 *Inpatient Pilot***

For the *inpatient pilot*, 20 patients will be enrolled. The inpatient pilot will be a non-randomized feasibility assessment of subcutaneous furosemide in the target study population. After stabilized in the hospital for at least 24 hours of IV diuretic therapy. Subjects in the inpatient pilot will receive subcutaneous furosemide for 48 hours, during which they will remain in hospital. This will be primarily a safety and feasibility assessment. There will be no formal hypothesis tested, and statistical analysis will be descriptive in nature. The specific goals of the inpatient pilot will be to:

- Test patient tolerability of subcutaneous delivery of furosemide in AHF population
- Develop and refine screening and recruitment strategies to identify the target study population.

### **5.2 *Outpatient Pilot***

For the *outpatient pilot*, an additional 20 patients will be enrolled. The outpatient phase will be a non-randomized feasibility assessment that will mirror the planned outpatient subcutaneous strategy planned for the larger trial. Eligible patients will be discharged home on either 80mg subcutaneous daily or BID (based on their anticipated diuretic requirements at the time of enrollment). Subcutaneous device therapy will continue for 1-7 days and dose (QD vs. BID) will be directed by the treating physician. Subjects in the outpatient pilot phase will have contact with the study site by telephone on D1, D3 and 5 days post enrollment. They will have a lab visit on D2 (+2d) post enrollment. They will have a clinic visit on D7 (+2d) post enrollment to assess the ability to utilize the subcutaneous device at home, the adequacy of diuresis, and resolution of signs and symptoms related to congestion. Subjects will have a D14 phone call to assess for adverse events. More frequent clinic contacts or laboratory monitoring may be performed as clinically indicated. A set of guidelines based on weight, symptoms, and subject-reported qualitative diuresis (see details in Appendix C) will be utilized in deciding when to transition from subcutaneous device therapy to oral diuretic therapy by the treating physician. Outpatients may not continue subcutaneous therapy beyond day 7.

The specific goals of the outpatient pilot will be to:

- Assess the feasibility of subcutaneous furosemide delivery in the target population in the outpatient setting, as measured by qualitative assessment of subject compliance and successful use of the device and related aspects of self-care (daily weights, blood pressure, etc.).
- Assess subject tolerability and safety of subcutaneous furosemide
- Assess and refine the planned guidelines for monitoring clinical response and adjustment of subcutaneous diuretics and transitioning to oral diuretics shown in Appendix C
- Assess and refine the frequency and nature of site interactions (phone calls, clinic visits, lab visits) that will be utilized in the Evaluation phase

At the completion of the pilot phase, the results will be reviewed by the HF Network Steering Committee and the Data and Safety Monitoring Board. The main SUBQ-HF study protocol will be amended, if needed, based on the analysis of the results from the pilot phase experience. If there are no substantive concerns about safety or feasibility, the SUBQ-HF study will proceed as designed.

## 6.0 STUDY FLOW DIAGRAM

Figure 6A. Inpatient Pilot Flow Diagram

[figure not shown]
[figure not shown]

Figure 6B. Outpatient Pilot Phase Flow Diagram

## **7.0 STUDY POPULATION AND ELIGIBILITY CRITERIA**

The study population for both the Inpatient and Outpatient Pilots will be identical. Patients hospitalized with acute heart failure (AHF) will be screened for participation in the study using the inclusion and exclusion criteria listed below.

### **7.1 Inclusion Criteria**

1. Age  $\geq$ 18 years
2. Willingness and ability to provide informed consent
3. Hospitalization for AHF with at least 1 symptom (dyspnea, orthopnea, or edema) AND 1 sign (rales on auscultation, peripheral edema, ascites, pulmonary vascular congestion on chest radiography, BNP > 250 ng/mL or NTproBNP > 1000 ng/mL) of congestion
4. Persistent congestion despite at least 18 hours of IV therapy, defined by the presence of at least 2 or more of the following *at the time of consent*:
  - a. Peripheral edema
  - b. Rales
  - c. Elevated JVP
  - d. Ascites
  - e. BNP > 250 ng/mL or NTproBNP > 1000 ng/mL
5. Total anticipated daily IV furosemide dose (at time of screening)  $\geq$ 80-200 mg (or equivalent)/day
6. Anticipated need for at least 24 more hours of parenteral diuretic therapy

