### ***10.1 Baseline Evaluation: Inpatient Pilot***

At the time of enrollment, all study subjects will undergo:

- Directed history and physical examination, focused on signs and symptoms of congestion
  - Vital signs (including weight)
  - NYHA Classification prior to decompensation
  - Input and Output measurement starts at enrollment (time of consent)
  - Review of concomitant cardiovascular medications, diuretics and electrolyte supplementation
  - Baseline NTpro-BNP or BNP, creatinine, BUN, and electrolytes (local laboratory), pregnancy test (if female and if not done during hospitalization)
  - Numerical rating score (0-10 point NRS) for symptoms (see **Appendix B**)
- Assessments and labs done as usual care within 4 hours of enrollment may be collected and entered into the eCRF for the study.

Once the baseline data points have been collected, a member of the study team will teach the subject about the subcutaneous pump and the infusion will be started.

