## **15.0 MONITORING**

The study will be monitored remotely by representatives of the Duke Clinical Research Institute or its designee according to the prospective clinical monitoring plan for the following purposes:

- To enable real-time monitoring of compliance with study protocol inclusion and exclusion criteria; this will be enabled via triggers and range checks programmed in the InForm database.
- To assist site personnel who will verify data identified within query reports against source documents through frequent telephone and email contact.
- To verify that written informed consent was obtained before initiation of any screening procedures that are performed solely for determining eligibility for the clinical study and/or prior to any tests or procedures.

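### The BNP and NT-proBNP cut-offs in inclusion criteria 3 and 4e are printed in ng/mL; if laboratories report in pg/mL, the unit is 1,000 times too high and the peptide item cannot be met as written

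*Combined protocol and SAP*

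**What the plan says.** Section 7.1 uses the peptides in two places, with the same numerals and the same unit.

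- Criterion 3 asks for "Hospitalization for AHF with at least 1 symptom (dyspnea, orthopnea, or edema) AND 1 sign" of congestion. The list has five signs: rales, peripheral edema, ascites, a radiographic finding, and the peptide threshold, "BNP > 250 ng/mL or NTproBNP > 1000 ng/mL".
- Criterion 4 covers congestion that persists at consent, "defined by the presence of at least 2 or more of the following": peripheral edema, rales, elevated JVP, ascites, and finally "e. BNP > 250 ng/mL or NTproBNP > 1000 ng/mL".

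The peptide is therefore an alternative in both criteria and is required in neither.

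Sections 10.1, 10.2 and 10.2.4 call for a BNP or NT-proBNP measurement at the local laboratory, and Appendix A schedules it. None of these places gives an assay, a reporting unit or a reference range.

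Section 5.0 states: "The same inclusion and exclusion criteria will be used for both phases of the pilot". Section 15.0 adds that compliance with the criteria is monitored in real time, and that "this will be enabled via triggers and range checks programmed in the InForm database".

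**The concern.** The numerals 250 and 1000 look like cut-offs on a pg/mL scale with the wrong unit attached. The documents do not state the scale, so this is an assumption drawn from general laboratory knowledge. The structure of the criteria points the same way. The peptide stands beside ordinary bedside findings as an equal alternative, so it was evidently meant to be something that patients with acute heart failure could meet.

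What is at stake is consistent eligibility. Criterion 4 is the plan's working definition of persistent congestion, and it applies to both phases (20 + 20 = 40 subjects). Read literally, it turns away a patient with one bedside sign and a clearly raised peptide. Read by numeral, it admits the same patient. With local laboratories at roughly 3 to 5 centers (section 2.0) and a programmed eligibility check, both readings could operate in one study. Section 5.1 also makes refinement of screening for the target population a goal of the inpatient phase, so an entry item that fails as written bears on something the pilot is meant to learn.

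**Working it through.** The plan has no sample-size or power figure to reproduce on this point, since the analysis is descriptive (section 12.1). The check is a unit conversion, a count, and an illustration.

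**Step 1: conversion.** 1 ng/mL = 1,000 pg/mL.

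- BNP: 250 × 1,000 = 250,000 pg/mL.
- NT-proBNP: 1000 × 1,000 = 1,000,000 pg/mL.

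An illustrative patient with rales and a BNP of 900 pg/mL has 0.9 ng/mL, far below the printed 250 ng/mL. That patient has 2 of the 5 findings in criterion 4 if the unit is pg/mL, and 1 of 5 as printed.

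**Step 2: what remains if the peptide item can never be met.** Count present/absent patterns over five items (2^5 = 32).

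| | Criterion 3 (at least 1 of 5) | Criterion 4 (at least 2 of 5) |
|---|---|---|
| Qualifying patterns | 32 − 1 = 31 | 32 − 1 − 5 = 26 |
| Lost without the peptide | 1 (peptide is the only sign) | 4 (one bedside sign plus peptide) |
| Still qualifying | 30 | 22 |

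Counted as minimal pairs for criterion 4, C(5,2) = 10 pairs qualify and C(4,2) = 6 of them do not use the peptide.

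Criterion 4 is where the loss bites. Anyone with two of edema, rales, elevated JVP and ascites has at least one of edema, rales or ascites, and each of those is also a listed sign in criterion 3.

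**Step 3: share of patients, illustration only.** The pattern counts are not patient shares, and the documents give no prevalence for any sign. Assume four independent bedside signs, each with prevalence q, and a peptide above the presumed pg/mL cut-off in a fraction b of patients, independently of the signs. Then

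- p1 = P(exactly one bedside sign) = 4q(1 − q)^3
- p2 = P(at least two bedside signs) = 1 − (1 − q)^4 − p1
- share lost on criterion 4 = b·p1 / (p2 + b·p1)

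Worked case, q = 0.5 and b = 0.7: p1 = 0.25, p2 = 0.6875, share = 0.175 / 0.8625 = 20.3%.

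| q | p2 | share lost, b = 0.7 | share lost, b = 0.9 |
|---|---|---|---|
| 0.3 | 0.348 | 45.3% | 51.5% |
| 0.4 | 0.525 | 31.6% | 37.2% |
| 0.5 | 0.688 | 20.3% | 24.7% |
| 0.6 | 0.821 | 11.6% | 14.4% |
| 0.7 | 0.916 | 5.5% | 6.9% |
| 0.8 | 0.973 | 1.8% | 2.3% |

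The denominator is patients who would satisfy criterion 4 with the peptide read in pg/mL. The range is about 2% to about 52%, driven almost entirely by the assumed q.

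**The case against.** The strongest reply is that this is a slip nobody would act on. The reporting scale is nowhere in the documents. Sites in a heart failure network would compare the numeral with the value on their own laboratory report and so enrol the patients the authors presumably had in mind. A range check programmed literally would flag every entry that relied on the peptide and expose the error, and sections 12.3.1 and 15.0 provide queries and verification against source. Section 15.0 does not say how the peptide field or its unit is programmed. No analysis uses the threshold.

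Much of this stands. The scale is an assumption: a laboratory that really reported on a ng/mL scale where 250 is an ordinary value would make the text correct. Sites would probably read the numeral, and the programming of the check is unknown. But the reply depends on sites departing from the approved wording of an operative entry rule. Any subject entered that way is, on paper, an eligibility deviation, and a flag that exposes the error during enrolment costs more than correcting it beforehand.

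A reader might go further and infer that the criteria themselves cannot be met. They can: 22 of 26 patterns for criterion 4 and 30 of 31 for criterion 3 survive without the peptide.

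**Conclusion.** The unit in criteria 3 and 4e needs correction, with minor to moderate importance. On the assumption of pg/mL reporting, the printed thresholds are 1,000 times too high and the peptide item is out of reach if read literally. The patients affected are those who need the peptide to qualify: exactly one bedside sign plus a raised peptide for criterion 4, or the peptide as sole sign for criterion 3. How many there are cannot be settled from the documents; the illustrative range assumes independent signs of equal prevalence and may be far from the truth in either direction.

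Two stronger conclusions are tempting and unsupported. One is that the trial would enrol a wrongly enriched population. The plan defines no biomarker enrichment or stratification, and sites that apply the numeral in their laboratory's own unit would enrol the presumed intended patients. The other is a count of affected subjects among the 20 in each phase. No prevalence is given from which to derive one, and each phase enrols 20 under either reading, with other patients taking the places of those turned away.

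No sample size, test or descriptive summary changes.

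**What to change.** Confirm the intended unit and, if it is as presumed, restate it as pg/mL (ng/L) for both peptides in section 7.1, items 3 and 4e. Make the eCRF unit field and the database range check use that unit, with an explicit conversion for any laboratory that reports differently. If any subject has already been entered on the peptide item, record which unit was applied.

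The cost is two lines of protocol text and one check of the database build. Procedures, patient numbers and analysis are untouched. Because the wording sits in an eligibility criterion, the sponsor should decide whether the correction counts as administrative under section 14.2 or needs ethics committee approval.
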